1 PROTOCOL SUMMARY

Objective	The objective of this study is to evaluate the reliability of the Ablacon Electrographic Flow (EGF) algorithm technology (Ablamap® Software) to identify AF sources and guide ablation therapy in patients with persistent atrial fibrillation
Test Device	Ablacon Electrographic Flow Algorithm Technology (Ablamap® Software)
Study Design	The study is a prospective, randomized, controlled multi-center study.
Planned Subject Sample Size	A maximum of 100 subjects will be enrolled in this study.
No. of Sites	Subjects will be enrolled at up to five (5) investigational sites in Europe.
Primary Safety Endpoint	Freedom from serious adverse events (SAEs) related to the procedure through 7 days following the Randomization procedure.
Primary Efficacy Endpoint	Acute procedure success defined as the ability to successfully ablate AF sources identified by the Ablacon EGF algorithm
Secondary Efficacy Endpoints	
 • Consistency of sources identified by the Ablacon EGF algorithm between the randomization procedure and any applicable subsequent EGF-guided ablation procedures as assessed by remapping of the atria and the algorithm's ability to reproduce sources identified by a previous procedure • Freedom from documented episodes of atrial fibrillation recurrence following the blanking period (90 days post procedure through 12 months). • Total number of EGF source ablations • Total time of EGF source ablations • Total fluoroscopy time and dose • Overall procedure time
Inclusion Criteria	
 1. Suitable candidate for intra-cardiac mapping and ablation of atrial arrhythmias. 2. Above eighteen (18) years of age or of legal age to give informed consent specific to state and national law. 3. Subjects with a history of documented symptomatic, persistent or longstanding persistent atrial fibrillation ≤ 36 months. 4. Subject agrees to comply with study procedures and be available (geographically stable) for follow-up visits for at least 12 months.

	
5. Treatment of atrial fibrillation with ablation therapy presenting with recurrent symptoms of AF (not applicable to De Novo subjects)
																
Exclusion Criteria	
 1. LA diameter > 5.5 cm. 2. Left ventricular ejection fraction (LVEF) < 35%. 3. Presence of intramural thrombus, tumor or abnormality that precludes vascular access, catheter introduction or manipulation. 4. Coagulopathy, bleeding diathesis or suspected procoagulant state. 5. Known allergies or intolerance to anticoagulant and antiplatelet therapies to be used in conjunction with the study or contrast sensitivity that cannot be adequately pre-treated prior to the ablation procedure. 6. Positive pregnancy test results for female patients of childbearing potential or breast feeding. 7. Acute or chronic medical condition that in the judgment of the investigator would increase risk to the patient or deem the patient inappropriate to participate in the study. 8. Mitral valve stenosis and/or severe mitral regurgitation. 9. Valvular atrial fibrillation. 10. Prosthetic valves. 11. NYHA Class IV. 12. History of MI within 3 months prior to procedure. 13. Atrial septal defect (ASD) or left atrial appendage (LAA) closure device. 14. Atrial fibrillation from a reversible cause (e.g., surgery, hyperthyroidism, sarcoidosis or pericarditis). 15. Life expectancy < 12 months based on medical history or the medical judgement of the investigator. 16. Presence of any transvenous pacing, ICD or CRT leads. 																
Follow-up Visit Schedule	
  
 Subject Visit Description	Timeframe / Visit Window	
   
 Randomization Procedure	Day 0	
 
 Pre-Discharge	Prior to discharge from hospital following ablation procedure	
 
 7 days Follow-Up (Phone)	7 ± 3 days	
 
 3 Month Follow-Up	90 ± 15 days	
 
 6 Month Follow-Up	180 ± 30 days	
 
 12 Month Follow-up	365 ± 45 days	
 
 Unscheduled Visits	As needed/necessary	
  
	Subject Visit Description	Timeframe / Visit Window	Randomization Procedure	Day 0	Pre-Discharge	Prior to discharge from hospital following ablation procedure	7 days Follow-Up (Phone)	7 ± 3 days	3 Month Follow-Up	90 ± 15 days	6 Month Follow-Up	180 ± 30 days	12 Month Follow-up	365 ± 45 days	Unscheduled Visits	As needed/necessary
Subject Visit Description	Timeframe / Visit Window																
Randomization Procedure	Day 0																
Pre-Discharge	Prior to discharge from hospital following ablation procedure																
7 days Follow-Up (Phone)	7 ± 3 days																
3 Month Follow-Up	90 ± 15 days																
6 Month Follow-Up	180 ± 30 days																
12 Month Follow-up	365 ± 45 days																
Unscheduled Visits	As needed/necessary																

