2 STUDY PROTOCOL

2.1 Objective

The objective of this study is to evaluate the reliability of the Ablacon Electrographic Flow (EGF) algorithm technology (Ablamap® Software) to identify AF sources and guide ablation therapy in patients with persistent atrial fibrillation.

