2.3 Secondary Endpoints

- Consistency of sources identified by the Ablacon EGF algorithm between the Randomization procedure and any applicable subsequent EGF-guided ablation procedures
- Freedom from documented episodes of AF recurrence following the blanking period (90 days post-ablation) through 12 months.
- Total number of EGF source ablations
- Total time of EGF source ablations
- Total fluoroscopy time and dose
- Overall procedure time

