2.6 Randomization

A 1:1 blocked randomization scheme stratified by site will be used for randomization. Subjects will be randomized based on the results of the pre-procedure EGF mapping procedure. If the subject has identifiable AF sources above a pre-specified threshold, the subject will be randomized to either: 1) immediate EGF-guided radiofrequency ablation with the Ablamap® Software System; or 2) EGF mapping followed by a cardioversion procedure, if required. If the subject is randomized to no treatment, the investigator may choose to cardiovert the subject prior to ending the procedure. Subjects that have no identifiable sources or sources below the threshold will not be randomized. The investigator may choose to ablate those subjects per their standard ablation practices.

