2.7 Statistical Analysis

Continuous variables will be reported as mean \pm standard deviation and where appropriate as median \pm interquartile range. Continuous variables were compared with unpaired t-test, and proportions were compared with the chi-square test. A two-sided p-value of $< .05$ was considered to indicate a statistically significant difference. For the secondary effectiveness endpoint of freedom from AF from the 90-day post-procedure blanking period through 12 months of follow-up, the length of time to recurrence of AF in each group was analyzed using Kaplan-Meier curves. Data were managed using Microsoft Excel and statistical analyses calculated using Microsoft Excel or Matlab.

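### The consistency endpoint is described only as earlier sources being found again, with no role for new sources and no chance reference, so it cannot separate repeatability from over-calling

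*Combined protocol and SAP*

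**What the plan says.** Section 2.1 sets the study objective: to "evaluate the reliability of the Ablacon Electrographic Flow (EGF) algorithm technology (Ablamap® Software) to identify AF sources" and to guide ablation. Of the listed endpoints, only the consistency endpoint bears on whether the algorithm gives the same answer twice.

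That endpoint is worded in two places. The Protocol Summary, under Secondary Efficacy Endpoints, says consistency between procedures is judged by remapping and by "the algorithm's ability to reproduce sources identified by a previous procedure". Section 2.3 lists only "Consistency of sources identified by the Ablacon EGF algorithm between the Randomization procedure and any applicable subsequent EGF-guided ablation procedures" and adds no measure.

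Section 2.7 gives the general methods: "Continuous variables were compared with unpaired t-test, and proportions were compared with the chi-square test", with Kaplan-Meier curves for AF recurrence. It names no agreement statistic. Nowhere do the documents say how a source seen only on the later map is counted, what region or distance makes two sources the same, what agreement chance would give, or what level would show reliability.

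**The concern.** The one description given runs in a single direction: was an earlier source seen again? A map that shows the earlier sources plus many new ones answers this as well as a map that shows the earlier sources alone. Nor is there a benchmark for how often a source would be found again if the algorithm placed sources without regard to the heart being mapped.

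This matters because the objective is reliability, and because Section 1.1 presents the software's advantage as telling active sources from passive rotations. Flagging too many sites is therefore a failure that a consistency measure ought to reveal. A rate computed as described could present it as reliability.

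**Working it through.** The documents state no consistency figure, target or expected number of remapped subjects, so there is no figure to reproduce. The check uses a simple model.

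**Inputs, all assumed.** R is the number of distinguishable locations, m the number of first-map sources, k the number of later-map sources and x the number on both maps. The documents give none of them. The 64-electrode basket in the Introduction is used only as an upper end for R.

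**Step 1: new sources.** The one-way reproduction rate is x/m. It does not contain k, so adding flagged sites to the later map can raise it (through x) but never lower it. Two-way measures do contain k: Dice = 2x/(m+k). Cohen's kappa over the R locations also uses k.

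Take m = 2, R = 16 and both first-map sources found again (x = 2):

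| k | One-way x/m | Dice 4/(2+k) | Kappa |
|---|---|---|---|
| 2 | 100% | 4/4 = 1.00 | 1.00 |
| 4 | 100% | 4/6 = 0.67 | 0.60 |
| 8 | 100% | 4/10 = 0.40 | 0.25 |
| 12 | 100% | 4/14 = 0.29 | 0.09 |

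For example, kappa at k = 8: observed agreement is (2+8)/16 = 0.625, and expected agreement is (2/16)(8/16) + (14/16)(8/16) = 0.50. Kappa is then (0.625 − 0.50)/(1 − 0.50) = 0.25.

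This effect needs k larger than m. If both maps flag the same number, Dice = 2x/(2m) = x/m, and the two scores coincide.

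**Step 2: chance.** If the k later sources fall at random among R locations, each first-map source is matched with probability k/R. That is the expected reproduction rate with no real repeatability:

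| R | k = 2 | k = 4 | k = 8 |
|---|---|---|---|
| 16 | 12.5% | 25% | 50% |
| 32 | 6% | 12.5% | 25% |
| 64 | 3% | 6% | 12.5% |

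If a subject counted as consistent when at least one source recurs, a rule the documents do not state, chance would give 1 − C(R−m, k)/C(R, k). With m = 2 and k = 8 this is 77% (R = 16), 44% (R = 32) and 24% (R = 64).

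**Step 3: can the planned methods correct this?** The unpaired t-test and chi-square test compare independent groups. They do not measure agreement between two maps of the same subject, and neither supplies a chance reference here.

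**The case against.** The strongest reply is that no score has been laid down at all. A reader might infer that the plan formally scores consistency one way and ignores new sources. The documents do not support that: there is no formula, consistency between two procedures is a symmetric phrase, Section 2.3 is neutral, and remapping would show new sources to anyone who looked. This stands as a limit on wording. The gap remains, because the only operational phrase given is one-way and nothing obliges the analyst to count the rest.

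Second, the effect may be small. With 64 locations and few flagged sites, chance reproduction is only 3% to 6%. Section 2.6 also refers to a threshold ("If the subject has identifiable AF sources above a pre-specified threshold") that could limit how many sites are flagged. Both points are fair. However, the matching resolution is not stated, and the threshold has no stated value and serves as a gate to randomization, with no link to this endpoint.

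Third, a pooled two-way score could mislead in the other direction. In the EGF-ablation arm the first-map sources are the ablation targets. A correct map after successful ablation should no longer show them, and new sources there may be real. This stands, and it shapes the remedy below.

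Fourth, this is one of six secondary endpoints, with no hypothesis or success level attached. That limits the severity, though it is the endpoint closest to the stated objective.

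**Conclusion.** The concern holds in this form: the consistency endpoint, as far as it is described, asks only whether earlier sources recur. A rate built on that description cannot distinguish a repeatable algorithm from an over-calling one. The direction follows from the definition and needs no assumption.

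The size cannot be derived from the documents. Under the assumed inputs, a constant 100% reproduction rate goes with Dice anywhere from 1.00 to 0.29, and chance alone gives about 3% (R = 64, k = 2) to 50% (R = 16, k = 8). With fine matching and few flagged sites the chance problem is minor; with coarse regions or many flagged sites it is serious.

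A reader might go further and conclude that the algorithm does over-call, or that a high consistency figure would be mostly chance. Nothing in the documents shows either. The change should be made, but the trial's primary endpoints do not depend on it.

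**What to change.** 1. Fix in advance the anatomical region or distance within which two sources count as the same.
2. For every remapped subject, report the number of sources on both maps, on the first map only and on the later map only, separately by randomized arm, with the number of remapped subjects in each.
3. Take the arm mapped without EGF-guided ablation as the main evidence on repeatability. In the ablation arm, the presence or absence of a first-map source may reflect the ablation.
4. Beside the reproduction rate, give a two-way agreement measure such as Dice or kappa, and the agreement expected by chance under the same matching rule. If maps are coded to common anatomical regions, obtain chance agreement by pairing each later map with other subjects' first maps; this also allows for sites that are common to many patients. Otherwise place the same number of sources at random, and say that this does not allow for common sites.
5. Give a 95% CI by resampling subjects.

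**Cost.** No new patient procedures are needed, since Section 1.1 describes software that works on saved recordings. The work is in wording, analysis code and some coding of regions; the documents describe no common region scheme, so one would have to be set up. The reported figure will probably look less favourable, and intervals will be wide if few subjects are remapped.

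### The recurrence endpoint counts only AF, so documented flutter or atrial tachycardia is scored event-free in either arm, while only one arm is ablated at the randomization procedure

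*Combined protocol and SAP*

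**What the plan says.** All three statements of the endpoint name AF and no other rhythm. The Protocol Summary has "Freedom from documented episodes of atrial fibrillation recurrence following the blanking period". Section 2.3 has "Freedom from documented episodes of AF recurrence following the blanking period (90 days post-ablation) through 12 months". Section 2.7 says that "the length of time to recurrence of AF in each group was analyzed using Kaplan-Meier curves".

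Atrial flutter and atrial tachycardia are not named as recurrence, failure, a competing event or a separate endpoint. Flutter appears only in the title of a cited reference. What counts as a documented episode is not defined by rhythm or duration.

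Section 2.6 describes the arms. One receives "immediate EGF-guided radiofrequency ablation with the Ablamap® Software System". The other receives "EGF mapping followed by a cardioversion procedure, if required", and the same section goes on: "If the subject is randomized to no treatment, the investigator may choose to cardiovert the subject prior to ending the procedure". Ablation by the investigator's usual practice is mentioned only for subjects who are not randomized.

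Table 1 in section 3.2 schedules a 12-lead ECG at 3, 6 and 12 months and a Holter at 6 and 12 months.

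**The concern.** An AF-only event treats a change from AF to another atrial arrhythmia as a success. If that change were equally common in both arms, the difference between arms would be unaffected. Here the arms differ, at the randomization procedure, in exactly the exposure that could influence which rhythm a subject has afterwards.

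The endpoint is labelled secondary, but it matters more than the label suggests. The primary effectiveness endpoint, and the number and time of source ablations, exist only where EGF sources are ablated. Source consistency, fluoroscopy and procedure time do not measure whether the patient's rhythm improved. AF recurrence is the only listed efficacy endpoint on which the randomized arms can be compared for patient outcome.

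The case will also need a ruling in practice. If a scheduled tracing after day 90 shows flutter and no AF, the text scores the subject as free. If the sponsor meant otherwise, nothing says so, and the choice would be made after the tracings are seen.

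**Working it through.** The plan gives no event rate, effect size or power for this endpoint, so there is no figure to reproduce. The check has two parts, and both rest on assumed rates.

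**1. Size of the misstatement**

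Take complete follow-up to 12 months. In each arm, let S be the share free of any atrial arrhythmia and f the share with flutter or tachycardia but no AF after day 90.

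- AF-only freedom in an arm = S + f
- AF-only difference = (S_EGF − S_control) + (f_EGF − f_control)
- Misstatement = f_EGF − f_control

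Assume f_EGF of 5-15% and f_control of 0-5%. Combined freely:

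| f_EGF | f_control | Misstatement (points) |
|---|---|---|
| 5% | 5% | 0 |
| 5% | 0% | 5 |
| 10% | 2% | 8 |
| 15% | 5% | 10 |
| 15% | 0% | 15 |

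The range is 0 to 15 points. If f_control exceeded f_EGF, the sign would reverse.

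**2. What such an excess could do to a comparison**

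Inputs:

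- Two-sided 0.05 and a chi-square test for proportions (section 2.7), with 1:1 allocation (section 2.6).
- n = 50 per arm, the most that the cap of 100 enrolled allows. 30 per arm is an assumption, for the case where some subjects are not randomized.
- True freedom from any atrial arrhythmia p = 51% in both arms. This is only an anchor, taken from the upper PVI success figure for persistent AF in the Introduction.
- An excess x of flutter- or tachycardia-only subjects in the EGF arm (assumption), and none in the control arm.

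The apparent AF-free share in the EGF arm is p1 = p + x. With m = (p1 + p)/2:

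- se0 = √(2m(1 − m)/n)
- se1 = √((p1(1 − p1) + p(1 − p))/n)
- P(significant for ablation) = Φ((x − 1.96·se0)/se1)

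For x = 10% and n = 50: p1 = 0.61 and m = 0.56. Then se0 = √(2 × 0.56 × 0.44/50) = 0.0993 and se1 = √((0.2379 + 0.2499)/50) = 0.0988. So Φ((0.10 − 0.1946)/0.0988) = Φ(−0.96) = 16.9%.

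| Excess x | Apparent AF-free, EGF v control | n = 50 per arm | n = 30 per arm |
|---|---|---|---|
| 0 | 51% v 51% | 2.5% | 2.5% |
| 5% | 56% v 51% | 7.2% | 5.8% |
| 10% | 61% v 51% | 16.9% | 11.8% |
| 15% | 66% v 51% | 32.9% | 21.5% |

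The last two columns give the chance of a significant result for ablation when the arms are truly equal on any atrial arrhythmia. With p = 30% or 40% the results are similar. For scale, the difference detectable with 80% power at 50 per arm from 51% is about 27 points, so a 15-point excess would be more than half of it.

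**The case against.** The strongest reply is that the documents nowhere say that ablation leaves or creates flutter or tachycardia, and give no rate for either arm. On the text alone, this is a narrow secondary endpoint, worded consistently and matched to its target: the objective concerns AF sources, inclusion criterion 3 requires AF, and section 2.4 requires subjects to be in AF at the procedure. That stands. It rules out calling this a contradiction, and it means that the size and direction cannot be derived from the documents. It does not remove the unscored outcome or the difference between arms at randomization.

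Three stronger readings are tempting, and the documents do not support them.

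- A reader might infer that the control arm cannot be scored falsely free. It can: a control with flutter and no documented AF is also event-free. Controls may also carry lesions from an earlier ablation (section 2.4 and inclusion criterion 5).
- A reader might infer that only one arm is ever ablated. The Protocol Summary and section 2.3 refer to later EGF-guided ablation procedures without saying which arm may have them. The asymmetry is certain only at the randomization procedure.
- A reader might see a conflict with inclusion criterion 1, "Suitable candidate for intra-cardiac mapping and ablation of atrial arrhythmias". That is a criterion of procedural suitability, and section 3.1.1 drops the word atrial. It does not define what the trial should score.

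The false-positive figures are also open to challenge. They presuppose the excess and use a test of proportions, whereas section 2.7 specifies only Kaplan-Meier curves for this endpoint. They illustrate sensitivity and do not estimate the trial's error rate.

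**Conclusion.** The point holds as a weakness of endpoint definition. As written, documented flutter or tachycardia without AF after day 90 counts as freedom in both arms, and the arms differ in ablation at the randomization procedure. The comparison could therefore credit a change of arrhythmia as freedom from arrhythmia. That this would favour ablation is plausible but is not established by the documents, and a claim that the bias certainly runs towards the device would go too far.

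The 0-to-15-point range depends wholly on the assumed shares. It includes no bias at all, so a narrower range should not be quoted. The primary endpoints are unaffected. The change is worth making because it protects the one between-arm comparison of patient outcome at little cost. Confidence is medium.

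**What to change.** Keep the AF-only endpoint unchanged. Add to section 2.7 a supportive analysis, specified before the data are examined:

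- Event: first documented atrial fibrillation, atrial flutter or atrial tachycardia from day 90 through 12 months, with day 90 counted from the randomization procedure in both arms.
- Method: Kaplan-Meier by randomized arm, reported beside the AF-only result, with the number in each arm whose only event is flutter or tachycardia.
- Source: the 12-lead ECGs and Holters already in Table 1. The 3-month window is ±15 days, so a 3-month ECG counts only if taken after day 90.
- Documentation: one sentence stating what makes an episode of each rhythm documented, applied identically in both arms.

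No visit, treatment or new success rule is needed. The cost is that tracings must be classified by rhythm, which the plan does not now provide for, and that the EGF result may look slightly less favourable. If the arms do not differ in these rhythms, the added analysis will support the AF-only result.

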2.2 Primary Endpoints

The primary endpoint events for this trial to assess the safety and effectiveness of the Ablamap® Software System to guide therapy for the treatment of persistent atrial fibrillation are as follows:

- Primary Safety Endpoint: Freedom from serious adverse events (SAEs) related to the procedure through 7 days following the Randomization procedure.
- Primary Effectiveness Endpoint: Acute procedure success defined as the ability to successfully ablate AF sources identified by the EGF algorithm.

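### Freedom from AF recurrence counts any documented episode, and the plan does not separate scheduled from unscheduled detection, so unequal checking by arm can distort the main randomised efficacy comparison in either direction

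*Combined protocol and SAP*

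**What the plan says.** The secondary endpoint in section 2.3 is "Freedom from documented episodes of AF recurrence following the blanking period (90 days post-ablation) through 12 months". The document does not define what makes an episode documented: the type of recording, its minimum duration and the occasion on which it was obtained are all left open.

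Table 1 (section 3.2) schedules post-discharge rhythm tests identically in both arms: a 12-lead ECG at 3, 6 and 12 months and a Holter at 6 and 12 months. The Protocol Summary adds unscheduled visits, with the timing given only as "As needed/necessary". Table 1 has no column for them, and no rule says whether their recordings count towards the endpoint.

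The Protocol Summary states that "The study is a prospective, randomized, controlled multi-center study". Section 2.6 compares immediate EGF-guided ablation with "2) EGF mapping followed by a cardioversion procedure, if required", and introduces the option of cardioversion in the second arm with the words "If the subject is randomized to no treatment". No section describes masking of subjects, investigators or rhythm readers, a core laboratory, or adjudication. Section 2.7 analyses time to recurrence with Kaplan-Meier curves and names no test for them.

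**The concern.** The endpoint depends on looking. A Kaplan-Meier curve of time to documented recurrence responds both to whether AF is found and to when. Scheduled testing is sparse, so some recurrences could first come to light at unscheduled visits. Subjects and investigators who know that no sources were ablated may have more reason to seek a recording. That would add control-arm events and bring them forward without any true difference.

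The endpoint is secondary, but it carries the comparison. The primary effectiveness endpoint is "Acute procedure success defined as the ability to successfully ablate AF sources identified by the EGF algorithm", which cannot be compared with an arm that is not ablated at that procedure. The other secondary endpoints concern source consistency and procedural quantities. Freedom from AF is therefore the main efficacy outcome on which the randomised arms can be set against each other.

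**Working it through.** **Inputs from the documents.** "A maximum of 100 subjects will be enrolled in this study", and "A 1:1 blocked randomization scheme stratified by site will be used for randomization", so there are at most 50 subjects per arm. Subjects without qualifying sources are not randomised (section 2.6) and the number randomised is not stated, so I use 25 to 50 per arm. Section 2.7 sets a two-sided 5% level and the chi-square test for proportions. The plan gives no planning rate, detection rate or power, so there is no figure of its own to reproduce.

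**Assumptions.** True recurrence T is 40-60%, the same in both arms. Scheduled tests find a share s of 50-70%. Unscheduled visits find a share u of the remainder: 30-50% in control and 10-30% in EGF.

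**Step 1: apparent recurrence.** In each arm this is T × [s + (1 − s) × u], so the spurious difference is T × (1 − s) × (u control − u EGF).

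- Lower end: u = 0.3 in both arms gives a difference of 0.
- Midpoint (T 0.5, s 0.6, u 0.4 v 0.2): control 0.5 × [0.6 + 0.4 × 0.4] = 0.38; EGF 0.5 × [0.6 + 0.4 × 0.2] = 0.34; difference 4 points.
- Most adverse (T 0.6, s 0.5, u 0.5 v 0.1): control 0.6 × [0.5 + 0.5 × 0.5] = 0.45; EGF 0.6 × [0.5 + 0.5 × 0.1] = 0.33; difference 12 points.
- Scheduled tests finding 90% (T 0.5, s 0.9, u 0.4 v 0.2): control 0.47; EGF 0.46; difference 1 point.

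**Step 2: false-positive rate.** With d the spurious difference, the two-sided rejection probability is approximately Φ[(d − 1.96 × SE0)/SE1] + Φ[(−d − 1.96 × SE0)/SE1]. SE0 uses the pooled proportion and SE1 the two separate ones. For the most adverse case with 50 per arm, SE0 = √(2 × 0.39 × 0.61/50) = 0.0975 and SE1 = √[(0.45 × 0.55 + 0.33 × 0.67)/50] = 0.0968. Then (0.12 − 0.191)/0.0968 = −0.74, which gives 23%.

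| Scenario | 25 per arm | 50 per arm |
|---|---|---|
| Midpoint | 6.0% | 7.0% |
| Most adverse | 13.8% | 23.2% |
| Scheduled tests find 90% | 5.1% | 5.1% |

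Exact binomial calculation of the chi-square test agrees closely: 6.8% and 7.0% at the midpoint, 15.8% and 23.8% in the most adverse case.

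**Step 3: timing and direction.** A log-rank simulation used 3,000 runs, 50 per arm, 50% true recurrence in both arms, visits at days 180 and 365, and unscheduled detection 14 days after onset. The nominal one-sided rate is 2.5%.

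- If scheduled visits miss nothing, so that only timing differs, a false EGF benefit appears in 4.7% of trials (u 20% EGF v 50% control) and 7.7% (10% v 60%).
- If each scheduled visit finds half, the figures are 12.7% and 26.0%.
- With half found and the gap reversed (60% EGF v 10% control), false EGF benefit falls to 0.1%, and a significant result against EGF appears in about 26% of trials.

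**Step 4: which safeguard works.** Under the Step 1 model, a scheduled-only analysis has expected recurrence T × s in both arms, and simulated false EGF benefit returns to about 2.5%. Requiring only that the two analyses agree in direction does little, because one is a subset of the other. With 50 per arm, T 0.5, s 0.5 and u 0.5 v 0.2, false benefit falls only from 11.9% to 11.5%; in the most adverse case it falls from about 24% to 22%.

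**The case against.** Scheduled testing is identical in both arms, the endpoint is secondary, and both primary endpoints are untouched. Subjects have persistent or longstanding AF and must be in AF at the procedure, so a sustained recurrence might well show on repeated ECGs and Holters. At 90% scheduled detection the problem almost vanishes. All of this stands as a limit on the size. It does not remove the gap, because equal scheduled testing does not control what is found, or how early, between visits.

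A reader might infer three stronger things, none of which the documents support.

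- **That the plan pools unscheduled with scheduled recordings in one curve.** Section 2.7 does not say so; unscheduled recordings are neither included nor excluded.
- **That the bias must favour EGF.** More checking in the control arm is plausible because that arm is openly unablated, but the opposite pattern would hide a benefit.
- **That serious error inflation is the expected case.** The assumed ranges include no difference at all. The 23% figure needs every input at its worst and all 100 enrolled subjects randomised, although section 2.6 leaves some unrandomised.

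**Conclusion.** The concern holds as a correctable weakness. With documented recurrence undefined, unscheduled visits open-ended and no masking described, following the plan as written can bias the main randomised efficacy comparison in either direction. Under the stated assumptions the spurious difference is 0 to 12 points. A central case is 4 points, with a two-sided error of about 6-7%; the extreme is about 14-23%. These figures rest on assumed detection rates and an assumed 25 to 50 subjects per arm. They show what could happen, not what will. The change is worth making because it is cheap and uses tests already scheduled.

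**What to change.** In section 2.7:

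1. Pre-specify a supporting between-arm analysis of AF freedom that uses only the scheduled ECGs and Holters of Table 1. Report its estimate and confidence interval beside the all-documentation Kaplan-Meier curve.
2. Describe a benefit as robust only if the scheduled-only estimate is of similar size, not merely in the same direction.
3. Count a subject re-treated for documented AF between visits as a recurrence in the scheduled-only analysis, or show the result both ways. Otherwise such a subject could be in sinus rhythm at the next scheduled test and be counted as free of AF.
4. Report unscheduled visits and rhythm recordings per arm.
5. Have whoever already reads the tracings do so with the arm label removed, where feasible.

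The cost is one extra analysis, a count by arm, and label removal on tracings already recorded. No visit or test is added. The scheduled-only analysis has fewer events and is less precise, so it supports the all-documentation analysis and does not replace it.
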